9.4.3 ANALYSIS OF THE SECONDARY ENDPOINT(S)

Descriptive statistics and two-sided 95% CIs of the difference between treatments will be computed for the following secondary endpoints:

- Incidence of endophthalmitis
- Proportion of patients without signs of anterior chamber inflammation (sum of cells and flare score = 0) after 3 and 7 days of treatment
- Proportion of patients with conjunctival hyperemia score equal to 0 after 3, 7 and 14 days of treatment
- Proportion of patients with TOSS score equal to 0 after 3, 7 e 14 days of treatment
- Proportion of patients with ocular pain/discomfort score equal to 0 after 3, 7 and 14 days of treatment
- Proportion of patients using rescue therapy during treatment

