1.3 SCHEDULE OF ACTIVITIES (SOA)

	Visit 1 Screening ^a -28 days max	Visit 2 Surgery	Visit 3 Day 4	Visit 4 Day 8	Visit 5 Day 15 (EOS)
Signed written	x				
informed consent	Λ				
Demography	X				
Medical history	X				
Inclusion/exclusion	v	v			
criteria	Λ	Λ			
Concomitant	v	v	v	v	v
medications	Λ	Λ	Λ	Λ	Λ
Urine pregnancy test ^b		X			
Surgery		Х			
Randomization ^c		X			
Dispensation of		v		\mathbf{v}^{f}	
treatment and diary		Λ		Λ	
Slit lamp examination ^d	X		Х	Х	Х
TOSS			Х	Х	Х
Diagnosis of endophthalmitis			Х	Х	X
Ocular pain and			Х	Х	X
			V	V	V
Use of rescue therapy	V		$\frac{\Lambda}{\mathbf{v}}$		A V
Intraocular pressure	Λ		Λ	Λ	Λ
Visual acuity (as per local practice)	X				Х
Local tolerability ^e			X	X	X
Adverse events	X	X	X	X	X
Return of treatment				X	X
Return of					
diary/compliance			Х	X	Х

TOSS = Total Ocular Symptoms Score; EOS = End of Study

Additional visits may be scheduled in case of patient need.

^a Screening to be performed not more than 28 days prior to surgery

^b A urine pregnancy test (dipstick) is required for women of childbearing potential.

^c Patients who complete surgery without complications will be randomized immediately after surgery.

^d Slit lamp examination of anterior chamber: cells score and aqueous flare (Tyndall effect) score; assessment of conjunctival hyperemia.

^e Global evaluation on a 4-point scale. Burning, stinging, blurred vision on a 4-point scale.

^f Second period of treatment will start after drug dispensation at Day 8

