5.2 EXCLUSION CRITERIA

An individual who meets any of the following criteria will be excluded from participation in this study:

- 1. Ocular conditions that at the discretion of the Investigator may interfere with the efficacy and/or safety evaluations (e.g. ocular herpes, blepharitis, conjunctivitis, uveitis, keratitis, diabetic retinopathy, retinal vein occlusions, retinal vasculitis, retinal angiomatous proliferation, pseudoexfoliation syndrome, intraoperative floppy iris syndrome, etc.)
- 2. Patients undergoing bilateral cataract surgery
- 3. Patients under treatment with prostaglandin analogues or intravitreal injections of anti-VEGF (vascular endothelial growth factor) drugs
- 4. Systemic diseases that may interfere with the results of the study (e.g. rheumatoid arthritis, Sjögren's syndrome, Behçet's disease, systemic lupus erythematosus, scleroderma with major ocular involvement, etc.)
- 5. Any condition that could interfere with correct instillation of eye drops
- 6. Ocular surgery in the study eye (including laser surgery) in the 3 months before screening
- 7. Monocular patients
- 8. Visual Acuity (VA) < 20/80 of the contralateral eye measured as ETDRS or Snellen 20 feet, equal to 0.25 in decimal
- 9. Contraindications to ocular treatment with Tobradex[®], Maxidex[®] or levofloxacin/dexamethasone as follows:
 - Herpes simplex keratitis, vaccinia, varicella and other viral diseases of the cornea and conjunctiva
 - Fungal and mycobacterial diseases of ocular structures or untreated parasitic eye infections
 - Uncontrolled intraocular hypertension
 - Uncontrolled glaucoma

Tobradex[®] is contraindicated also in case of untreated purulent infection of the eye, whereas Maxidex[®] is contraindicated in acute, untreated bacterial infections.

10. Hypersensitivity to the study product or its excipients

- 11. Participation in other clinical studies if at least 5 half-lives of the IMP used in the previous studies have not passed between the end of treatment in the previous study and the start of treatment in this clinical study.
- 12. Pregnancy or breastfeeding

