8.2 EFFICACY ASSESSMENTS

• Slit lamp examination

A slit lamp examination will be performed at Visit 1 (screening) and on Day 4 (Visit 3), Day 8 (Visit 4), and Day 15 (Visit 5) to evaluate cells in the anterior chamber and aqueous flare as follows:

Cells in anterior chamber: results are to be provided as a score: 0 = no cells; 1 = 1-5 cells; 2 = 6-15 cells; 3 = 16-30 cells; 4 = >30 cells.⁴⁸

Aqueous flare (Tyndall effect): results are to be provided as a score: 0 = absent; 1 = trace barely detectable; 2 = mild intensity (iris and lens details clear); 3 = moderate intensity (iris and lens details not clear); 4 = strong intensity (iris and lens details not visible and fibrin in the anterior chamber).⁴⁴

Conjunctival hyperemia will be evaluated and results provided as a score as follows: 0 = absence of inflammation, 1 = mild inflammation (some vessels injected), 2 = moderate inflammation (diffuse injection of vessels, but individual vessels are still discernable) 3 = severe inflammation (intense injection of vessels, individual vessels not easily discernable).⁴⁵

• Endophthalmitis

All cases of endophthalmitis occurring following cataract surgery are to be reported at all visits.

• Total Ocular Symptom Score (TOSS)

The TOSS is a patient-reported evaluation of 3 ocular symptoms: itching/burning, hyperemia of conjunctiva and tearing. Each symptom is given a score: 0 = none, 1 = mild, 2 = moderate, 3 = severe. The TOSS will be evaluated on Days 4, 8, and $15.^{46}$ See Appendix 1.

• Ocular pain/discomfort

Overall ocular pain and discomfort will be evaluated by the subject at Days 4, 8 and 15 on a 4-point scale (0 = absent, 1 = mild, 2 = moderate, 3 = severe).

• Use of rescue therapy

All rescue therapy used following cataract surgery is to be reported at all visits (see *Section 6.5.2*).

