9 STATISTICAL CONSIDERATIONS

9.1 STATISTICAL HYPOTHESES

The primary objective of the trial is to demonstrate the non-inferiority of combined levofloxacin + dexamethasone for 7 days followed by dexamethasone alone for an additional 7 days vs. standard treatment tobramycin + dexamethasone for 14 days in the prevention and treatment of postoperative ocular inflammation and prevention of infection.

The primary endpoint is the proportion of patients without signs of anterior chamber inflammation (sum of cells and flare score = 0) after 14 days of treatment. The following non-inferiority hypotheses will be tested:

 $H_0: \boldsymbol{\pi}_T - \boldsymbol{\pi}_S \leq \textbf{-} \Delta$

 $H_1: \boldsymbol{\pi}_T - \boldsymbol{\pi}_S > \textbf{-} \Delta$

Where π_T and π_S are the proportions of patients without signs of anterior chamber inflammation in the test and standard treatments, respectively, and the non-inferiority margin is $\Delta = 10\%$.

Secondary endpoints:

- Incidence of endophthalmitis
- Proportion of patients without signs of anterior ocular chamber inflammation after 3 and 7 days of treatment
- Conjunctival hyperemia after 3, 7 and 14 days of treatment
- Total Ocular Symptoms Score (TOSS) after 3, 7 and 14 days of treatment
- Ocular pain/discomfort after 3, 7 and 14 days of treatment
- Use of rescue therapy during treatment

No formal statistical hypotheses will be tested for the secondary endpoints.

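### The conjunctival hyperemia comparison leaves the collected screening score unused, so its 95% CI is somewhat wider than one adjusted for that score

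*Combined protocol and SAP*

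**What the plan says.** Section 9.4.3 lists "Proportion of patients with conjunctival hyperemia score equal to 0 after 3, 7 and 14 days of treatment" among the secondary endpoints. The analysis for the whole list is: "Descriptive statistics and two-sided 95% CIs of the difference between treatments will be computed for the following secondary endpoints". No covariate or baseline term is named. Section 9.1 adds: "No formal statistical hypotheses will be tested for the secondary endpoints".

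The score exists before surgery. In the Schedule of Activities (Section 1.3) the slit lamp row is ticked at screening, and footnote d describes that examination as "Slit lamp examination of anterior chamber: cells score and aqueous flare (Tyndall effect) score; assessment of conjunctival hyperemia". Section 8.2 confirms that it is done at Visit 1 as well as on Days 4, 8 and 15. It grades hyperemia from 0 to 3, with 0 meaning no inflammation.

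Eligibility sets no limit on the screening score. The nearest criterion is the first exclusion in Section 5.2: "Ocular conditions that at the discretion of the Investigator may interfere with the efficacy and/or safety evaluations". Conjunctivitis and blepharitis appear there as examples. Section 9.4.1 mentions baseline efficacy data only to say that the arms will not be tested against each other on them.

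**The concern.** The objective concerns inflammation after surgery. Some eyes may already be mildly red at screening, and those eyes are less likely to reach 0 afterwards in either arm. An outcome that depends on a known baseline value carries variation that the analysis could remove. Leaving it in makes the interval for the difference between arms wider than the data require.

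The rule also gives the same result to two different eyes: one that scores 0 at screening and 1 on Day 15, and one that scores 1 at both visits. Both count as not cleared, though only the first is redder than at screening.

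At stake is how precisely the trial describes hyperemia in the two arms. Adjustment is best fixed before data are seen, because choosing it later would be post hoc.

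**Working it through.** **The plan's own figure.** The protocol gives no precision target for hyperemia. Its only size calculation (Section 9.2) is for the primary endpoint: (1.96 + 0.8416)² × 2 × 0.64 × 0.36 / 0.10² = 361.7, so 362 per group, as stated. Dividing 724 by 0.90 gives 805 against the stated 800, consistent with a dropout rate of about 10%. I use 362 evaluable patients per arm below.

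**Inputs not in the documents (assumptions).** Let k be the share of eyes with screening hyperemia of 1 or more. Let a be the share scoring 0 after treatment among eyes that scored 0 at screening, and c the same share among eyes red at screening. The arms are taken as equal.

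**Formulas.**
- Overall rate: P = a(1 − k) + ck.
- Share of outcome variance explained by screening status: R² = k(1 − k)(a − c)² / [P(1 − P)].
- Unadjusted half-width: 1.96 × √[2P(1 − P)/362].
- Large-sample adjusted half-width: the unadjusted one times √(1 − R²). The narrowing is 1 − √(1 − R²).

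**Worked case, a = 0.75, c = 0.15, k = 0.10.** P = 0.675 + 0.015 = 0.69. R² = 0.09 × 0.36 / (0.69 × 0.31) = 0.0324 / 0.2139 = 0.151. The narrowing is 1 − √0.849 = 7.9%. In percentage points the half-width goes from 6.74 to 6.21.

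**Range.**

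| Clearing, a vs c | k = 5% | k = 10% | k = 20% |
|---|---|---|---|
| 75% vs 15% | 4.3% | 7.9% | 13.2% |
| 75% vs 45% | 1.1% | 2.0% | 3.4% |
| 50% vs 10% | 1.5% | 2.9% | 5.4% |
| 30% vs 6% | 0.7% | 1.3% | 2.5% |

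For 75% vs 45% the half-width changes from 6.43 to 6.36 points at k = 5%, and from 6.74 to 6.51 at k = 20%. Rows 1, 3 and 4 hold c at one fifth of a, so they show the gain falling as overall recovery falls.

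**What adjustment does not do.** Suppose 20% of eyes are red at screening and none can reach 0, while the arms differ by 10 points in the rest. The difference over all eyes is 0.80 × 10 = 8.0 points. A stratum-weighted estimate gives 0.80 × 10 + 0.20 × 0 = 8.0 as well. Adjustment changes the precision, not the estimand, and the eye scoring 1 before and 1 after still counts as not cleared.

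**The case against.** The strongest reply is that nothing here is invalid. Score 0 is the scale's own absence of inflammation, the rule is the same in both arms and matches the other score-0 endpoints in Section 9.4.3, and an unadjusted risk difference is sound in a randomised trial. The named exclusions should keep screening redness uncommon, and the steroid in both arms may clear some of it. Screening may be up to 28 days before surgery, so the score is an imperfect reference. Section 9.3 also leaves missing-value methods to a statistical analysis plan, so a supportive table there cannot be ruled out. All of this stands. It limits the size of the point but does not remove it: a baseline value is collected and the described analysis does not use it.

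A reader might infer three stronger things that the documents do not support.

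- **That requiring a score of 0 widens the interval in general.** Compare it with a different endpoint, return to the screening score or better, reached by a share p, and let a share b be red at screening and never reach 0. With equal arms, the score-0 interval is wider only if p exceeds 0.5 and b is below 2 − 1/p. With b = 10% the half-width goes from 0.0583 to 0.0654 at p = 0.80, but from 0.0668 to 0.0647 at p = 0.30. The width claim holds only against the adjusted interval for the same endpoint.
- **That attenuation eases a non-inferiority conclusion on hyperemia.** Section 9.1 sets no hypothesis or margin for this endpoint, so no decision is loosened. Randomisation balances screening redness in expectation, so neither arm is favoured.
- **That eyes with cells or flare at screening inflate false non-inferiority on the primary endpoint.** If 5% of eyes could never clear, rates of 0.64 and 0.54 in the others would give −10 × 0.95 = −9.5 points overall. Section 9.1 defines its hypotheses on the proportions in each treatment, not in a subset of clearable eyes. A true −9.5 is inside the margin, and concluding non-inferiority would be correct.

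**Conclusion.** The point stands as a missed and modest gain in precision. The unadjusted interval for hyperemia is wider than the adjusted one whenever screening redness predicts later redness. For 5% to 20% of eyes red at screening, the excess that adjustment would remove is about 1% to 3% of the width under a weak contrast (75% vs 45% clearing) and 4% to 13% under a strong one (75% vs 15%). It is less at low recovery rates. These figures rest on assumed prevalence and clearance, because the documents supply neither; if no eye is red at screening, the gain is zero. The endpoint is secondary and descriptive. The primary analysis and the sample size are unaffected.

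**What to change.** In Section 9.4.3, keep the score-0 endpoint at all three time points. Estimate the risk difference and its 95% CI adjusted for screening hyperemia (0 versus 1 or more), using a stratum-weighted or standardised method. Tabulate the screening scores by arm.

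Optionally, add a supportive summary of the proportion whose score is no higher than at screening. Only this summary, not the adjustment, deals with the eye that scores 1 before and 1 after surgery. It should stay supportive, since it would also count an eye scoring 2 at both visits as a success.

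The cost is a paragraph of analysis wording and a few tables, with no new data, visits or patients.

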3 OBJECTIVES AND ENDPOINTS

OBJECTIVES	ENDPOINTS	JUSTIFICATION
Efficacy		FOR ENDFOINTS
To demonstrate the non-inferiority of combined levofloxacin + dexamethasone eye drops for 7 days followed by dexamethasone eye drops alone for an additional 7 days vs. standard treatment tobramycin + dexamethasone eye drops for 14 days in the prevention and treatment of postoperative ocular inflammation and prevention of infection.	 Primary endpoint The proportion of patients without signs of anterior chamber inflammation (sum of cells and flare score = 0) after 14 days of treatment Secondary endpoints Incidence of endophthalmitis Proportion of patients without signs of anterior ocular chamber inflammation after 3 and 7 days of treatment Conjunctival hyperemia after 3, 7 and 14 days of treatment Total Ocular Symptoms Score (TOSS) after 3, 7 and 14 days of treatment Ocular pain/discomfort after 3, 7 and 14 days of treatment Use of rescue therapy during treatment 	The endpoints are considered suitable for evaluating ocular inflammation and infection following cataract surgery.
Safety and tolerability		
To evaluate the safety of combined levofloxacin – dexamethasone eye drops.	 Intraocular pressure (IOP) Visual acuity Adverse events 	The safety endpoints are considered standard for the indication and for the drugs under study.
To evaluate the tolerability of combined levofloxacin – dexamethasone eye drops.	Global evaluationBurning, stinging, blurred vision	The endpoints are considered suitable for evaluating the tolerability of an ophthalmic product.
Compliance		
To evaluate compliance with prescribed treatment.	Assessment of patient diary	

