12 APPENDICES

APPENDIX 1: TOTAL OCULAR SYMPTOMS SCORE (TOSS)

TOSS Questionnaire

Please answer the following questions by marking the box that best represents your answer:

Have you experienced any of the following, and if so with what intensity?	None	Mild	Moderate	Severe
1. Itching/burning?				
2. Redness?				
3. Tearing (eyes watering)?				

TOSS Questionnaire Scoring

Total Ocular Symptom Score

1. Add up scores for the three symptoms.

None = 0

Mild = 1

Moderate = 2

Severe = 3

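### Section 9.4.3 compares TOSS, conjunctival hyperemia and ocular pain/discomfort between arms only as score zero or not, so no planned between-arm estimate reflects severity above zero

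*Combined protocol and SAP*

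**What the plan says.** Section 3 lists "Total Ocular Symptoms Score (TOSS) after 3, 7 and 14 days of treatment" as a secondary endpoint, and lists conjunctival hyperemia and ocular pain/discomfort at the same times. Section 9.1 repeats the list. Neither section names a cut.

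Section 8.2 defines the measurements. For TOSS, "Each symptom is given a score: 0 = none, 1 = mild, 2 = moderate, 3 = severe", and Appendix 1 gives the total: "Add up scores for the three symptoms". Three items of 0-3 make a total of 0-9. Hyperemia (graded at the slit lamp) and pain/discomfort (graded by the patient) each run from 0 to 3.

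Section 9.4.3 then plans a descriptive summary and a two-sided 95% CI for the treatment difference. For TOSS, the quantity compared is "Proportion of patients with TOSS score equal to 0 after 3, 7 e 14 days of treatment". The other two scores, redness and pain/discomfort, are cut at zero in the same way and compared at the same three visits.

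It names no mean, shift or ordinal comparison. Section 9.4.1 has categorical data summarised by frequencies and percentages. Section 9.1 states that no formal hypotheses are tested for the secondary endpoints.

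**The concern.** The only planned between-arm comparison of these scores uses one threshold on each scale. Suppose every patient in one arm who is above zero has mild symptoms, every such patient in the other arm has severe symptoms, and the proportions at zero are equal. The planned difference is then 0, and its CI is the same as if the arms were identical.

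What is at stake is the sensitivity of the symptom and redness comparisons. Under Section 6.1.2 the test arm uses the new combination only for the first 7 days and then changes to dexamethasone alone. The Day 4 and Day 8 assessments are therefore the ones made after the new product only. If few patients have reached zero by then, the cut is least sensitive at those visits. Whether few have done so is not known from the document.

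**Working it through.** **The plan's own figure.** The only sample-size figure is for the primary endpoint (Section 9.2): rate 0.64 in both arms, margin 0.10, one-sided 0.025, power 80%.

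n = (1.960 + 0.842)² × 2 × 0.64 × 0.36 / 0.10² = 361.7, so 362 per arm and 724 in total, as stated. 724 / 0.90 = 804.4, against 800 for a dropout of about 10%. The 0.64 is the Day 15 cells-plus-flare rate. It gives no information on TOSS, hyperemia or pain, or on earlier visits.

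**Inputs for the check.** From the document: the scale ranges and the cut at zero. Assumed, because the document gives no values: the share at zero, p0, and the spread of patients over the levels above zero. The spread was varied geometrically, with each level holding 0.2 to 1.0 times the one below it.

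**Formula.** With 1:1 allocation and N patients in total, the information on a log odds ratio is:
- cut at zero: N × p0(1 − p0) / 4
- full ordinal score under proportional odds: N × (1 − Σp_k³) / 12

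Share kept by the cut = 3 p0(1 − p0) / (1 − Σp_k³).

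**Worked case.** Take a 0-3 scale with p0 = 0.10 and ratio 0.5. The level shares are 0.100, 0.514, 0.257 and 0.129, so Σp_k³ = 0.156. Share kept = 3 × 0.10 × 0.90 / 0.844 = 0.32.

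**Results over all spreads, share of ordinal information kept:**

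| Share at zero | 0-3 scale | 0-9 scale |
|---|---|---|
| 5% | 16-26% | 14-26% |
| 10% | 29-44% | 27-43% |
| 20% | 51-67% | 49-66% |
| 30% | 67-80% | 65-79% |
| 50% | 87-93% | 86-93% |
| 60% | 93-96% | 92-96% |
| 80% | 99% | 98-99% |

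TOSS simulated as the sum of three correlated 0-3 items (correlation 0.3 and 0.6) agrees: 30% kept at 11% zero, 45-49% at 18-20%, 62-69% at 28-32%, and 91-94% at 55-62%.

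**What this means for detecting a shift.** Assume 362 per arm, odds ratio 1.5, a 0-3 scale and ratio 0.5. The chance that a two-sided 95% CI excludes no difference is Φ(ln 1.5 × √information − 1.96). At p0 = 0.10 the information is 724 × 0.09 / 4 = 16.3 for the cut and 724 × 0.844 / 12 = 50.9 for the full score.

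| Share at zero | Cut at zero | Full ordinal score |
|---|---|---|
| 10% | 37% | 82% |
| 20% | 59% | 84% |
| 30% | 71% | 85% |
| 50% | 78% | 83% |
| 64% | 74% | 77% |

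A second model gives the same pattern for mean TOSS. It assumes latent-normal items with correlation 0.5, a 0.2 SD shift and 400 per arm. The chances, cut against mean, are 43% vs 92% at 11% zero, 58% vs 90% at 20%, 71% vs 89% at 37%, and 71% vs 79% at 64%.

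**Interval width.** With 362 per arm, the half-width of the 95% CI for a difference in proportions is 1.96 × √(2 p0(1 − p0)/362). This is 4.4 points at 10% zero, 5.8 at 20%, 7.3 at 50% and 7.0 at 64%. The intervals are narrowest where the cut loses most, so the weakness is insensitivity to severity and not imprecision of the proportion.

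**The case against.** The case for leaving the plan alone has real weight.

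- *The endpoints are descriptive.* No margin, test or error rate attaches to them, and non-inferiority rests on the primary endpoint alone (Section 9.4.2). This stands, and it limits the importance of the point.
- *The cut is a legitimate choice.* Freedom from a sign or symptom is easy to read and has the same form as the primary endpoint (cells plus flare equal to zero). Section 3 gives hyperemia and pain/discomfort no metric at all, so Section 9.4.3 can be seen as supplying one rather than contradicting it. This stands, and it is why the zero proportions should be kept.
- *Severity appears elsewhere.* Section 9.4.1 may yield frequency tables of every level, listings are planned, and rescue use, adverse events by severity and local tolerability are also reported. This stands only in part. Frequency tables carry no between-arm estimate, and the other outputs concern other variables.

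A reader might infer that few patients are at zero on Days 4 and 8, and so that most of the information is discarded. The document does not support this. Section 2.2 gives irritation of up to 98%, but for the first postoperative hours. The same section describes recovery as usually free of pain, which points the other way for pain. More than half of the information is lost only if about 20% or fewer score zero.

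A reader might also infer that early visits are where the products are most likely to differ. Section 4.2 says that both combinations carry the same anti-inflammatory component at the same concentration, so this is not established either.

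**Conclusion.** The point holds as a conditional one. Section 9.4.3 provides no between-arm estimate of severity for three graded scores, and no other section fills the gap. Under proportional odds the full score never carries less information than the cut. The cut keeps roughly 30-45% of the information if 10% of patients score zero, 50-67% at 20%, about 87-93% at 50%, and about 93% or more at 60% and above. The loss could therefore be large at one visit and negligible at another.

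These figures assume an effect that is similar across the scale. A treatment effect confined to reaching zero would favour the cut. The zero rates and spreads are assumed throughout.

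Two further readings go too far. One is that the planned intervals will be wide: half-widths are about 4 to 7 points. The other is that the cut could bias the trial towards non-inferiority: the primary analysis does not use these scores. The effect is confined to descriptive secondary results, and the change is a cheap improvement.

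**What to change.** In Section 9.4.3, keep the proportions at zero and add, at Days 4, 8 and 15:
- the full distribution of each score by arm;
- the between-arm difference in mean TOSS with two-sided 95% CI;
- for hyperemia and for pain/discomfort, one ordinal summary with 95% CI, either a common odds ratio or a probability index, chosen in advance.

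Adjusting hyperemia for its screening score is not needed. That examination precedes surgery by up to 28 days in patients screened for interfering eye conditions, so it would probably add little.

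The cost is a few more tables and more secondary estimates to report and interpret. No new data, visits or patients are required. Fixing the summaries before unblinding also avoids a post hoc choice among them.
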